6.6 Toxicity

A brief written summary documenting the toxicity or adverse reactions after the 6th patient (phase I study) has received his/her 3th dose will be prepared with input from the UCD clinical PI. The brief report will summarize and define if the study should continue or be terminated. At the end of Phase II study, a summary will likewise be completed to address the same issues. A recommendation whether to continue onto a Phase II clinical trial will also be included.

Toxicity assessments will be done by the treating physician or their licensed representative (such as nurse practitioner) on the days of therapy.

Patients with progressive disease will be counseled as to the option of exiting the study. They will be advised on their disease progress and future options, and their response, if any, to the therapy.

6.7 Criteria for Removal from Protocol Treatment

- Unacceptable toxicity (as determined by the treating physician and/or the patient), or toxicity requiring discontinuation of treatment (See sections 4.0 and 4.1).
- Elevation in AST or ALT $>20x$ ULN on bloodwork prior to CD24Fc treatment.
- Elevation of total bilirubin $>5x$ ULN on bloodwork prior to CD24Fc treatment.
- If the recovery of any $\geq G3$ hematologic or non-hematological toxicity due to CD24Fc to grade 1 or less requires > 2 weeks.
- Patients may choose to withdraw from the study at any time for any reason.
- Patients may be withdrawn from the protocol at the investigator's discretion if the investigator feels that continuation is not in the patient's best medical interest or if the patient is non-compliant with treatment.
- Completion of treatment CD24Fc.
- All reasons for discontinuation of treatment must be documented in the case report forms.
- Therapy after Protocol Treatment is stopped: If patients fail to respond to the protocol treatment and/or are removed from the therapy because of toxic effects or "disease progression", further treatment, if any, is at the discretion of the investigator.

Follow-up off Protocol Treatment: After removal from protocol treatment, all patients will be followed for late toxicities. Patients will be seen 4 weeks, 4 months and 7 months after coming off therapy. If ongoing toxicities have not resolved to \leq grade 1 within the first 4 weeks, patients are to be seen every month until toxicity resolves to \leq grade 1. No new toxicities after the 4-week follow-up will be re-reported unless considered related to protocol treatment by the investigator.

6.8 Replacement of Removed Patients

Additional patients are allowed to replace patients who choose to withdraw from the study before or within 28-day course of drug administration or patients who were withdrawn from the study at the investigator's discretion. Patients who are removed due to CD24Fc related DLT will not be replaced.

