	
Demographic and background characteristics obtained at enrollment will be listed and summarized. Descriptive statistics will be used to summarize changes of biomarkers from baseline in clinical laboratory parameters for this cohort, and use of steroids (drug, dose, duration) and other treatment for irAE.
 
To assess toxicity: Toxicity is evaluated by NCI CTCAEv5.0. The type, grade, frequency and proportion of toxicities noted during the treatment period will be reported, along with associated 95% confidence interval of proportion. All adverse events noted by the investigator will be tabulated according to the affected body system. In phase I lead-in study, dose limiting toxicity is defined as any new AE of \geqgrade 3 that are outside the spectrum of irAEs.
 
To assess time to recovery from irAE (time to reduction of irAE by at least one grade), time to all irAEs reduced to \leq1, and time to resume ICI treatment: The date of starting treatment (i.e., Day 1) will be used for all time events in the study. Kaplan-Meier plots and confidence intervals will be used to summarize outcomes. Medians and associated 95% confidence intervals will be calculated, and comparisons between groups will be performed by log-rank tests. Cox proportional hazard models will be used to explore association between covariates and outcomes.
 
To assess recovery rate of irAE by CD24Fc (reduction of irAE by one grade) at D42 and response rate of ICI: The fractions will be reported along with 95% two-sided confidence intervals. Comparisons between arms will be performed by Fisher's Exact tests. We will also characterize the proportion who remain that either respond or have stable disease, compared to those who progress.
 
To assess PFS and OS: Kaplan-Meier plots and confidence intervals will be used to summarize PFS, and OS; 1-year OS rate will be reported; medians and associated 95% confidence intervals will be calculated, and comparisons between groups will be performed by log-rank tests. Cox PH models will be used to explore association between outcomes and covariates.
 
As exploratory analysis, we will summarize descriptively the relationship of response rates to tumor type (lung, GI, melanoma, breast, prostate) and to cellular immune response and explore the relationship using logistic regression.

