	
The possibility of bias from missing data will be addressed. Missing pattern and mechanism will be evaluated, and sensitivity analyses will be performed using imputation methods for use of steroid, irAE type, cancer type, etc., if such might affect point estimates and study conclusions.
 
Sample Size Justification
 
Phase I study:
 
We plan to enroll 6 patients in the phase I study. The objective of this phase I study is to confirm the safety of CD24Fc in ICI-treated cancer patients who have treatment interruption due to grade 2 or 3 irAEs and to estimate the median time to recovery and resumption of ICI after treatment interruption due to irAE. The primary endpoint is new AE of \geqgrade 3 that are outside the spectrum of irAEs when CD24Fc is given to treat irAEs. We expect the rate of this event will be less than 33.3%. With a sample size of 6 patients, we would have 74-91% chance to observe at least one occurrence if the true event rate is 20-30%. Hence the sample size is adequate for this pilot study for safety.
 
Randomized phase II study:
 
Previous studies suggested that response rate at 42 days for control group will be about 50%. We hypothesize CD24Fc will increase recovery rate from 50% to 80 %. A sample size of 72 patients (36 in each arm) will have 81% power to detect an increase of recovery rate from 50% of control group to 80% of CD24Fc group. This result is based on one-sided Fisher's Exact test and significance level of 0.05. Group-sequential design will be used with interim analysis to monitor the trial by a cohort size of 24 (12 in each group), with maximum sample size of 72, average sample size of 46 if null hypothesis is true, and 58 if alternative hypothesis is true.
 
Steroids is the most commonly used SOC therapy for irAEs. It affects the severity and duration of irAE, which are the key endpoints of this study. We thus will stratify the subjects based on the status of steroids use at registration and will adjust steroids use in analyses. Few patients might start on steroids as SOC before starting the study treatment, and the patients will be moved to the steroid stratum.

Estimated Accrual/Enrollment Period:	Six patients in the phase I study and 72 patients in phase II randomized study. Of about 50 cancer patients received ICI per month at UCD, 8 patients (15%) develops grade 2 and 3 irAE that require treatment interruption. We estimate 4-5 patients will be enrolled each month.

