10. STATISTICAL CONSIDERATIONS

10.0 Endpoints

10.0.0 Primary Endpoints

Phase I: Event of new AE of \geq grade 3 that are outside the spectrum of irAEs when CD24Fc is given in cancer patients who developed grade 2-3 irAEs.

Phase II: Co-primary endpoints:

- Recovery rate (as defined by reduction of irAE by one grade) at Day 42.
- Time to recovery from grade 2 or 3 irAE (as defined by reduction of at least 1 grade in irAE severity) from the initiation of CD24Fc treatment. Patients who have not been documented to have event (reduction of at least 1 grade) will be censored at the date of the latest clinical assessment that documented as being free of event.

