10.1 Randomization for Phase II Study

Steroids is the most commonly used SOC therapy for irAEs. It affects the severity and duration of irAE, which are the key endpoints of this study. We thus will stratify the subjects based on the status of steroids use at registration. Stratified block randomization will be used. Randomization codes will be generated in a permuted block design, stratified by the status of steroids use at registration. The block size will be balanced within each block to maintain a 1:1 ratio between the two groups. For patient who have no steroids use at registration but start on steroids before starting CD24Fc treatment, the patient will be moved to the steroid stratum. If a subject withdraws from participation in the study or changed to steroids use group, his or her randomization code will not be re-used.

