10.2 Statistical Analysis

Demographic and background characteristics obtained at enrollment will be listed and summarized. Descriptive statistics will be used to summarize changes of biomarkers from baseline in clinical laboratory parameters for this cohort, and use of steroids (drug, dose, duration) and other treatment for irAE. We will adjust steroids use in analyses. Subgroup analyses will be performed separately by the status of Steroids use.

To assess toxicity: Toxicity is evaluated by NCI CTCAEv5.0. The type, grade, frequency and proportion of toxicities noted during the treatment period will be reported, along with associated 95% confidence interval of proportion. All adverse events noted by the investigator will be tabulated according to the affected body system. In phase I lead-in study, dose limiting toxicity is defined as any new AE of \geq grade 3 that are outside the spectrum of irAEs.

To assess time to recovery from irAE (time to reduction of irAE by at least one grade), time to all irAEs reduced to ≤ 1 , and time to resume ICI treatment: All time points will be started from Day 1 of CD24Fc treatment. Kaplan-Meier plots and confidence intervals will be used to summarize outcomes. Medians and associated 95% confidence intervals will be calculated, and comparisons between groups will be

performed by log-rank tests. Cox proportional hazard models will be used to explore association between covariates and outcomes.

To assess recovery rate of CD24Fc (reduction of irAE by at least one grade) at D42 and response rate of ICI: The fraction of patients who experience a PR or CR will be determined by dividing the number of responders by the total evaluable patients. The fraction will be reported along with 95% two-sided confidence intervals. Comparisons between groups will be performed by Fisher's Exact tests. We will also characterize the proportion who remain that either respond or have stable disease, compared to those who progress.

To assess PFS and OS: Kaplan-Meier plots and confidence intervals will be used to summarize PFS, and OS; 1-year OS rate will be reported; medians and associated 95% confidence intervals will be calculated, and comparisons between groups will be performed by log-rank tests. Cox PH models will be used to explore association between outcomes and covariates.

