As exploratory analysis, we will summarize descriptively the relationship of response rates to tumor type (lung, breast, prostate) and to cellular immune response, and explore the relationship using logistic regression.

The possibility of bias from missing data will be addressed. Missing pattern and mechanism will be evaluated, and sensitivity analyses will be performed using imputation methods for use of steroid, irAE type, cancer type, etc., if such might affect point estimates and study conclusions.

The study design in the Phase II portion allows steroids and other systemic treatments prior to and during study enrollment. CD24Fc/placebo will be added in addition to standard of care. We will perform a sensitivity test for data from the Phase II study. We will consider isolating the effect of CD24Fc in the future Phase III clinical study.

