10.4 Safety Monitoring and Stopping Rule

The Phase II study is a randomized, double blind, placebo-controlled study. To ensure the safety of the patients enrolled in the Phase II study, Bayesian stopping boundaries are used to allow early stopping at any given time in the combined population. The objective response rate (ORR) and toxicity of CD24Fc during the whole study will be monitored simultaneously using the Bayesian stopping boundaries calculated based on beta-binomial distribution. Toxicity is defined as new AE of \geq grade 3 that are

outside the spectrum of irAEs. ORR is defined as partial response and complete response by RECIST V1.1 after retreatment with ICI.

The regimen will be considered safe if the ORR is at least 20% in all patients in both arms and the toxicity rate is maintained at most 33.3% for the CD24Fc arm. Previous studies for controls suggested the ORR after retreatment with ICI is about 20-40%, and therefore we consider a response rate <20% in all patients in both arms as unacceptable, which will indicate an effect of CD24Fc on promoting tumor growth. The prior probabilities of response and toxicity for the regimen are modeled by beta distributions [Beta(0.8, 1.2) and Beta(0.3, 1.7), respectively], and response and toxicity are assumed to be independent. Denoting the probabilities of response for both arms and toxicity for CD24Fc arm by $\{\theta_{RES}, \theta_{TOX}\}$, and they are compared to fixed targets of response and toxicity rates. The following decision criteria will be applied:

- 1) stop if $\text{Prob}\{\theta_{RES} < 0.2 \mid \text{data}\} > 0.97$, and
- 2) stop if $\text{Prob}\{\theta_{TOX} > 0.333 \mid \text{data}\} > 0.97$

We will have randomization box of 6 patients and thus ensure that 3 patients have been dosed for each 6 subjects enrolled. Patients will be monitored by a cohort size of 6 patients (3 for the CD24Fc arm and 3 for the placebo arm) according to the following stopping boundary for toxicity during the whole study. To be conservative, we attribute all AEs to CD24Fc.

Number of Patients Evaluated in All Enrolled Patients (half control and half CD24Fc)	Stop if Number of ORR Observed	Stop if Number of AE Observed
6	Never stop with these many patients	Never stop with these many patients
12	Never stop with these many patients	≥ 5
18	0	≥ 7
24	≤ 1	≥ 8
30	≤ 2	≥ 10
36	≤ 2	≥ 11
42	≤ 3	≥ 12
48	≤ 4	≥ 14
54	≤ 5	≥ 15
60	≤ 6	≥ 16
66	≤ 7	≥ 17
72	Always stop with this number of patients	

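### Phase II does not say that withdrawn patients stay in the co-primary comparison or how a missing Day 42 grade counts, and its named tests do not deliver the promised steroid adjustment

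*Combined protocol and SAP*

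**What the plan says.** **Replacement.** Section 6.8 states: "Additional patients are allowed to replace patients who choose to withdraw from the study before or within 28-day course of drug administration". It extends this to patients withdrawn at the investigator's discretion and excludes only removals for a CD24Fc-related DLT. It names no phase.

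**Randomisation code.** Section 10.1 states: "If a subject withdraws from participation in the study or changed to steroids use group, his or her randomization code will not be re-used". It does not say whether the patient remains in the analysis.

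**Sample size.** The synopsis describes a group-sequential design "with maximum sample size of 72, average sample size of 46 if null hypothesis is true". The last row of the table in 10.4, at 72 patients, reads "Always stop with this number of patients". Neither place says whether 72 counts randomised or evaluated patients.

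**Denominator.** The paragraph of 10.2 that covers both Day 42 recovery and ICI response gives only this: "The fraction of patients who experience a PR or CR will be determined by dividing the number of responders by the total evaluable patients". That is worded for tumour response. Intent-to-treat appears only in the abbreviation list.

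**Missing data.** The synopsis and 10.2 say that bias from missing data will be addressed and that "sensitivity analyses will be performed using imputation methods for use of steroid, irAE type, cancer type, etc". The Day 42 grade is not named. Time to recovery does have a rule, in 10.0.0: it is measured "from the initiation of CD24Fc treatment. Patients who have not been documented to have event (reduction of at least 1 grade) will be censored", with the latest assessment as the censoring time. The synopsis adds: "The date of starting treatment (i.e., Day 1) will be used for all time events in the study".

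**Follow-up after removal.** Section 6.7 has removed patients seen 4 weeks after coming off therapy, then monthly while toxicity is unresolved. Table 2 schedules a Day 42 visit.

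**Steroid stratum.** Randomisation is stratified by steroid use at registration. The synopsis and 10.2 promise adjustment for steroid use, and 10.2 adds subgroup analyses. The tests named are Fisher's exact and log-rank, with no stratification mentioned. Cox models are for exploration. A patient who starts steroids before dosing is moved to the steroid stratum.

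**The concern.** Two readings are open for a Phase II patient who withdraws: keep the patient in the assigned arm, or drop the patient and count a replacement towards 72. The second gives up the comparison that randomisation protects. Withdrawal at the investigator's discretion turns on the patient's medical interest or compliance (6.7), so it may well follow the course of the irAE, which is the outcome itself. If it does, and the arms differ, the remaining patients are no longer comparable. If the choice is made after unblinding, it could depend on the results.

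The stratification issue is separate and has a different effect. The protocol itself says that steroids affect the severity and duration of irAEs. A comparison that does not use the stratum loses power when the strata recover at different rates; it does not inflate the type I error.

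**Working it through.** **Inputs from the plan (10.3):** 36 per arm, recovery 50% vs 80%, one-sided Fisher test at 0.05, stated power 81%. **Assumed, because the documents give none:** withdrawal rates, the share of withdrawals who are non-recoverers, and differences between steroid strata. A single final analysis is modelled; the interim analyses are not.

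**1. The plan's own figure.** Enumerating both binomials and rejecting when the one-sided hypergeometric tail is at most 0.05 gives power 80.9%, which agrees with 81%. The size at 50% in both arms is 3.8%. Both figures take a Day 42 outcome as known for all 36 per arm.

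**2. Recovery among those who remain.** With true recovery p, withdrawal rate w and share f of withdrawals who are non-recoverers, the rate becomes (p − w(1 − f))/(1 − w). With p = 0.5 in both arms and w = 15% (CD24Fc) vs 5% (control):

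- f = 0.75: (0.5 − 0.0375)/0.85 = 54.4% vs (0.5 − 0.0125)/0.95 = 51.3%, a spurious difference of 3.1 points.
- f = 1: 0.5/0.85 = 58.8% vs 0.5/0.95 = 52.6%, a spurious difference of 6.2 points.
- f = 0.5 (unrelated to recovery): 50% in both arms, no bias.

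**3. Patients per arm.** Codes are not re-used, so replacements take new 1:1 codes. Then 72 evaluated patients split as 72 × 0.85/1.80 = 34 and 72 × 0.95/1.80 = 38. Without replacement, 36 × 0.85 ≈ 31 and 36 × 0.95 ≈ 34 remain.

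**4. Size of the one-sided Fisher test (true recovery 50% in both arms).**

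| Withdrawn patients left out | No bias | f = 0.75 | f = 1 |
|---|---|---|---|
| Replaced, 34 vs 38 | 3.1% | 5.6% | 9.3% |
| Not replaced, 31 vs 34 | 2.7% | 4.9% | 8.3% |

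With the withdrawal rates reversed between arms, the bias runs against CD24Fc: in a simplified 36 vs 36 calculation the size falls from 3.8% to 2.1% (f = 0.75) or 1.0% (f = 1). With equal withdrawal of 5–20%, it is 3.4–3.8%.

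**5. One possible missing-data rule: not recovered if missing.** With withdrawal independent of outcome, power is computed at 0.8(1 − w) vs 0.5(1 − w), 36 per arm: 76.0% at w = 5% and 71.2% at w = 10%. This rule is not neutral either. If withdrawal is unrelated to recovery, the size is 8.8% at 5% CD24Fc vs 15% control (0.475 vs 0.425), and 1.4% reversed.

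**6. Stratified tests.** Two equal strata of 18 per arm are assumed. The exact test uses a common odds ratio of 4, which takes 50% to 80%; the log-rank test uses a hazard ratio of ln 0.2/ln 0.5 = 2.32, one-sided, because the plan states no side.

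| Control recovery by stratum | Fisher → exact stratified | Log-rank → stratified log-rank |
|---|---|---|
| 50% / 50% | 80.9% → 80.9% | 92.9% → 92.6% |
| 40% / 60% | 79.0% → 79.3% | not computed |
| 30% / 70% | 72.3% → 74.7% | about 82% → 90% |

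The exact-test figures come from full enumeration. The log-rank figures come from 40,000 simulated trials each (simulation error 0.1–0.2 points), with exponential recovery and assessment on Days 14, 28, 42 and 60.

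**The case against.** - **Section 6.8 may be meant for Phase I.** Its DLT exception uses a term that 4.1 defines for Phase I. That reading is plausible, but 6.8 does not state it, and 10.1 expressly foresees withdrawal of randomised patients.
- **Follow-up limits the missing outcomes.** This stands. Under 6.7, a patient removed on Day 14 would be seen at about Day 42, and Table 2 keeps a Day 42 visit. A reader might infer that everyone who stops treatment early loses the endpoint; the documents do not support that. They still give no analysis rule, and a patient who withdraws consent may not return.
- **Replacement is not the main cause.** This also stands. Leaving withdrawn patients out without replacing them gives nearly the same inflation (4.9% and 8.3%), so the defect lies chiefly in 10.2. Restricting 6.8 alone would remove little of it.
- **The plan may not substitute at all.** A reader might infer that it drops or swaps withdrawn patients. It does not say so; it leaves the choice open. Double blinding also makes large differences in withdrawal between arms less likely.
- **Steroid use is not ignored.** Adjustment and subgroup analyses are promised. What is missing is a method for the co-primary tests. Subgroup analyses do not adjust the overall comparison, and the gain for the exact test is small unless the strata differ widely.

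**Conclusion.** The point holds as a gap to close in advance, not as a demonstrated error. No text keeps a withdrawn randomised patient in the co-primary comparison, and no text says how a missing Day 42 grade counts. If such patients are left out, the consequence depends wholly on assumed withdrawal. At 15% vs 5%, the size rises to 5.6–9.3% with replacement or 4.9–8.3% without, against 3.1% and 2.7% when there is no bias. The lower end is close to the nominal 5%. Equal or unrelated withdrawal causes no inflation, and reversed rates bias against CD24Fc. A reader might infer that the trial will produce a false positive; the documents give no withdrawal rates to support that.

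The stratification point is a separate and lesser one. It concerns lost power only: small for the exact test, and about 8 points for the log-rank test under an assumed 30% vs 70% split.

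**What to change.** 1. **Synopsis and 10.2:** analyse every randomised patient in the assigned arm for both co-primary endpoints, with the 6.7 follow-up data used for the Day 42 grade where available. Keep the censoring rule for time to recovery. Because its clock starts at Day 1 of treatment, state the origin for a patient randomised but never dosed.
2. **Synopsis and 10.2:** state one primary rule for a Day 42 grade that is still missing, and one sensitivity analysis under a different assumption. Counting missing as not recovered is one option, but it is not neutral, so the second analysis is needed whichever rule is chosen. Report withdrawals and reasons by arm.
3. **Section 6.8:** state that Phase II replacements never substitute for randomised patients, and whether 72 counts all randomised patients.
4. **Synopsis and 10.2:** name an exact stratified (Mantel-Haenszel type) test and a stratified log-rank test, by steroid stratum, as the co-primary tests.
5. **Synopsis and 10.1:** reconcile this with the sentence that moves patients to the steroid stratum. State which stratum the analysis uses and that such patients keep their assigned arm.

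**Cost:** wording, plus a restated power. If missing counts as not recovered and withdrawal is independent of outcome, power is 76–71% at 5–10% withdrawal, and restoring 80% would take 42 or 46 per arm. Power stays at 81% if those patients would not have recovered anyway. The stratified tests need no extra patients or data.
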